#### **EVALUATION OF DISTRIBUTIONS OF OUTCOME VARIABLES.**

1. Variables will be examined for normality and Blom-transformed (percentiles to z-scores) for cases where violations compromise the interpretation of inferential statistics. Analyses will be conducted with and without these adjustments to assess whether such adjustments alter conclusions.

#### **EFFICACY ANALYSES FOR PRIMARY & SECONDARY OUTCOME VARIABLES**

Analyses Immediately following training

1. We plan 4 arms (Brain HQ, Rise of Nations, Driving and Fraud Avoidance Training, Puzzle Solving) x 2 times of measurement (baseline, post-training) ANOVAs (or ANCOVAs) for the following primary variables: fraud detection accuracy score, Driving Hazard Perception Test (safety and accuracy of navigation), Self-reported IADL task, Speed of Processing.

2. We plan 4 arms (Brain HQ, Rise of Nations, Driving and Fraud Avoidance Training, Puzzle Solving) x 2 times of measurement (baseline, post-training) ANOVAs (or ANCOVAs) for the following secondary variables: Technology Proficiency (CPQ & MDPQ average z-scored variables), Numeracy (accuracy on Berlin Numeracy Test), Reasoning Ability (average z-scored variables for Letter Sets & Ravens), Memory Ability (Average z-scored variables for Hopkins Verbal Learning Test and Rey Auditory Verbal Learning Test), Miami IADL task.

#### Analyses following one-year follow-up

3. We plan 4 arms (Brain HQ, Rise of Nations, Driving and Fraud Avoidance Training, Puzzle Solving) x 2 times of measurement (baseline, 1-year follow-up) ANOVAs (or ANCOVAs) for the following primary variables: fraud detection accuracy score, Driving Hazard Perception Test (safety and accuracy of navigation), Self-reported IADL task, Speed of Processing, Knowledge about Driving (accuracy), Knowledge about Finances and Fraud (accuracy).

4. We plan 4 arms (Brain HQ, Rise of Nations, Driving and Fraud Avoidance Training, Puzzle Solving) x 2 times of measurement (baseline, 1-year follow-up) ANOVAs (or ANCOVAs) for the following secondary variables: Technology Proficiency (CPQ & MDPQ average z-scored variables), Numeracy (accuracy on Berlin Numeracy Test), Reasoning Ability (average z-scored variables for Letter Sets & Ravens), Memory Ability (Average z-scored variables for Hopkins Verbal Learning and Rey Auditory Verbal Learning Test), Miami IADL task.

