Hi, this is [your name] from the CREATE lab at FSU. Is _____ there? Last [date of Post Testing] you completed your Post Testing for the Comparative Effectiveness project and we are coming up on the date for your Year Follow Up appointments. I was wondering if you had a couple minutes for us to schedule those two appointments to our lab? These appointments would need to be scheduled after [Post 1 month/day]. (Each appointment is an hour and a half to 2 hours and they will be given the remaining \$40 in compensation)

Alright, great so you're all scheduled. Our address is [name]. When you come, just drive up to the roundabout and someone will be there to meet you. Can you tell me the color and model of your car so we can recognize you?

If you have any questions please call [contact]. Thank you.

Support

ADVERSE EVENTS

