#### **EVALUATION OF RANDOM ASSIGNMENT**

1. We plan to compare the 4 arms at baseline on the variables of age, education level, and gender and on the primary and secondary outcome variables (MANOVA across variables) to assess if random assignment resulted in equivalence across groups. If it did not, then we plan to use ANCOVAs in the next stage rather than ANOVAs, controlling for baseline differences on these variables.

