### COMPARATIVE EFFECTIVENESS ANALYSES

#### Analyses immediately following training

1. Immediate gain scores (post-training - baseline)/hours of reported training, for above primary and secondary variables will be compared across Arms.

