#### Analyses following one-year follow-up

2. Long-term gain scores (1-year follow-up - baseline)/hours of reported training, for above primary and secondary variables will be compared across Arms.

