### EXPLORATORY ANALYSES OF INDIVIDUAL DIFFERENCE PREDICTORS OF GAIN

We will use multiple regression analyses to predict the above post-test and 1 year gain scores on primary and secondary variables from age, education, gender, occupation, expectation for improvement, and study arm.

---

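### For the nine outcomes planned at both time points, no one-year analysis uses the post-training score and no missing-data method is stated, so people lost between the two visits would ordinarily add nothing at one year

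*SAP*

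**What the plan says.** The Protocol (Overall design) has three assessments: baseline, after four weeks of training, and 12 months.

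- **After training.** The SAP's efficacy section plans four arms "x 2 times of measurement (baseline, post-training) ANOVAs (or ANCOVAs") for four primary and five secondary outcomes.
- **One year, efficacy.** A separate set of analyses uses four arms "x 2 times of measurement (baseline, 1-year follow-up) ANOVAs (or ANCOVAs") for the same nine outcomes plus two more primary ones, "Knowledge about Driving (accuracy), Knowledge about Finances and Fraud (accuracy").
- **ANOVA or ANCOVA.** The choice rests on the baseline comparison of arms. If they differ, "we plan to use ANCOVAs in the next stage rather than ANOVAs, controlling for baseline differences on these variables". The covariates are baseline variables only.
- **One year, comparative effectiveness.** "Long-term gain scores (1-year follow-up - baseline)/hours of reported training" are compared across arms. The immediate counterpart is "Immediate gain scores (post-training - baseline)/hours of reported training".
- **Exploratory regressions.** These "predict the above post-test and 1 year gain scores on primary and secondary variables from age, education, gender, occupation, expectation for improvement" and study arm. The post-training score is not a predictor.

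Neither document states a missing-data method, an analysis population or a likelihood-based model.

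**The concern.** A two-occasion ANOVA, an ANCOVA and a gain score, as usually run, all need the 12-month value. A person seen after training but not at 12 months would enter the baseline check, the post-training analyses and the immediate gain analyses, but no one-year comparison. Their post-training score is the most recent information on how they were doing, and it goes unused.

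Such people can exist. The follow-up call script (Protocol, Call Scripts) tells the participant "you completed your Post Testing for the Comparative Effectiveness project and we are coming up on the date for your Year Follow Up appointments", so anyone lost at that call has a post-training visit on file. The script does not show how much loss comes earlier.

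At stake is the one-year comparison, which the SAP lists for primary outcomes. If loss differs between arms, in rate or in how it depends on scores, the planned contrast can be biased. Which planned analysis is affected depends on what drives the loss, and the plan has no step that would show this, not even retention by arm.

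**Working it through.** **1. Count of outcomes.** Post-training: 4 primary + 5 secondary = 9. One year: 6 primary + 5 secondary = 11. All 9 are in both lists; the other 2 are the knowledge tests. Of the three kinds of one-year analysis (efficacy, gain per hour, regression), none uses the post-training score.

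**2. Inputs.** The documents give no figure to reproduce, so everything below is assumed: unit variances; correlations 0.70 (baseline-post), 0.70 (post-12 months), 0.65 (baseline-12 months); true 12-month difference 0.30 SD; lower scorers leave; loss follows post-testing.

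**3. Which analysis is exposed.** Write B, P and Y for the baseline, post-training and 12-month scores. The arm-by-time contrast averages Y - B. Baseline ANCOVA in effect averages Y - 0.65B. Loss that differs by arm biases an analysis when this quantity covaries with the driver of loss.

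| Driver | Covariance with Y - B | Covariance with Y - 0.65B |
|---|---|---|
| P | 0.70 - 0.70 = 0 | 0.70 - 0.65×0.70 = 0.245 |
| P - B | (0.70 - 0.65) - (0.70 - 1) = 0.35 | (0.70 - 0.65) - 0.65×(0.70 - 1) = 0.245 |
| B | 0.65 - 1 = -0.35 | 0.65 - 0.65 = 0 |

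**4. Size.** Simulation, two arms, 2 million per arm. Dropout logit = intercept - slope × driver, with the intercept set to give the stated rate. There are four loss patterns (the second arm has the benefit): 10% vs 20% and 13.5% vs 33%, score-related in both arms; 10% vs 29% and 20% vs 20%, score-related in the second arm only. Ranges cover the four patterns; the truth is 0.30.

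| Driver | Slope | Change contrast | Baseline ANCOVA | Three-occasion model |
|---|---|---|---|---|
| P - B | 1 | 0.33-0.39 | 0.32-0.36 | 0.30 |
| P | 1 | 0.30 | 0.32-0.36 | 0.30 |
| B | 1 | 0.21-0.27 | 0.30 | 0.30 |
| P - B | 0.3 | 0.31-0.33 | 0.31-0.32 | 0.30 |
| P | 0.3 | 0.30 | 0.31-0.32 | 0.30 |
| B | 0.3 | 0.27-0.29 | 0.30 | 0.30 |

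With 20% loss in each arm and the same dependence, all three give 0.30.

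The zero for the change contrast when P drives loss needs equal covariances. At slope 1, correlations of 0.80/0.65/0.60 (same order as in step 2) give 0.26-0.29, and 0.60/0.75/0.55 give 0.31-0.34. With correlations of 0.70/0.70/0.65 but a 12-month SD of 1.2, the covariance is 1.2×0.70 - 0.70 = 0.14 and the contrast is 0.31-0.34.

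**5. Precision.**
- Baseline adjustment: the variance factor is 2(1 - 0.65) = 0.70 for change and 1 - 0.65² = 0.5775 for ANCOVA. The ratio is 0.825, so about 17.5% lower (simulated at an assumed 60 per arm: 17-18%).
- Adding the post-training visit: the variance is multiplied by 1 - d·r², where d is the share lost after post-testing and r the partial correlation of P and Y given B. Here r² = (0.70 - 0.70×0.65)² / [(1 - 0.70²)(1 - 0.65²)] = 0.0600/0.2945 = 0.204. The gain is 2.0% at d = 10% and 4.1% at d = 20%.
- Over d = 10-30% and r = 0.3-0.7 the gain runs from about 1% to 15%.

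**6. Where the model fails (slope 1).**
- Loss driven by P or P - B, half of it before post-testing: model 0.31-0.33. All of it before: the model equals ANCOVA, 0.32-0.36.
- Loss driven by a stable unobserved trait: change 0.30, model 0.31-0.33, ANCOVA 0.32-0.36.
- Loss driven by later decline (Y - P): change 0.33-0.39, ANCOVA 0.33-0.39, model 0.34-0.42.

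**The case against.** The strongest reply is that no harm is shown. The documents report no attrition, and nothing in them indicates that loss differs by arm. Without such a difference there is no bias; with weak dependence it is 0.01-0.03 SD. That stands, and it limits how hard the point can be pressed.

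Three further objections also stand:
- The largest deviation in the table, 0.21-0.27 under baseline-driven loss, is not caused by ignoring the post-training visit. Baseline ANCOVA, which uses no post-training data, already returns 0.30. Most of the precision gain likewise comes from baseline adjustment.
- The drivers in the table are all observed before loss, which favours the three-occasion model by construction. When later decline drives loss, the model is further from the truth than either planned analysis.
- The ANCOVA figures describe a conditional analysis. The SAP uses ANCOVA only if arms differ at baseline, and adjustment for the same outcome's baseline score is not assured.

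A reader might also infer that the SAP prescribes a complete-case analysis or discards the post-training data. It does neither. Exclusion is inferred from how these methods are usually run, and the post-training scores have their own analyses.

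What the objections do not remove is the gap itself: an unstated missing-data rule, and a collected visit that cannot inform the one-year contrast.

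**Conclusion.** The point holds as a gap in the plan, not as demonstrated bias. For the nine shared outcomes, people lost between post-training and 12 months would ordinarily contribute nothing to the one-year comparison.

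The size of any bias is unknown. On the assumed inputs, strong arm-differential loss following the post-training score or early gain puts baseline ANCOVA off by 0.02-0.06 SD and the change contrast off by 0-0.09 SD. A three-occasion model removes this if loss follows post-testing. The precision credited to the post-training visit is small, about 2-4%; the 17-18% gain over the change analysis belongs to baseline adjustment.

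A reader might conclude that the one-year results will be biased, or that the mixed model is always safer. The documents support neither: they are silent on the amount, timing and cause of loss, and the ranking of methods depends on that cause. The case for change is that it uses data already collected at little cost. It is a recommended improvement, held with medium confidence.

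**What to change.** For the nine shared outcomes:
- Make the main efficacy analysis one longitudinal mixed model with baseline, post-training and 12 months. Include all randomised participants in their assigned arm, with unstructured covariance and a common baseline mean. Take both the post-training and the 12-month arm contrasts from it.
- Let this replace the conditional ANOVA/ANCOVA switch for these outcomes, since the common baseline mean supplies the baseline adjustment.
- Keep the planned two-occasion analysis as a sensitivity analysis, and state who is included in it.
- Add one delta-shift analysis for departures from missing-at-random.
- Report retention by arm and visit.

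The gain-per-hour analyses, the exploratory regressions and the two knowledge outcomes listed only at one year are outside this change.

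The cost is SAP wording and standard software; no new data are needed. The model relies on missing-at-random given the observed scores. It cannot correct outcome-related loss before post-testing and can do worse than the planned analyses if later decline drives loss. That is why the planned and delta-shift analyses stay beside it.

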### COMPARATIVE EFFECTIVENESS ANALYSES

#### Analyses immediately following training

1. Immediate gain scores (post-training - baseline)/hours of reported training, for above primary and secondary variables will be compared across Arms.

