Age-related perceptual and cognitive declines are associated with difficulties performing everyday tasks required to remain independent [1]. Encouraging improvements in cognitive abilities have been shown for a variety of short-term interventions such as group and individual training on abilities (e.g., the ACTIVE trial; [46]), digital games [6, 23], aerobic exercise [26], and combined treatments [5]). The rationale for these interventions is that they can be expected to support the maintenance of functional independence in older adulthood given the relatively strong relationship between Instrumental Activities of Daily Living (IADLs) performance and cognitive abilities [1], and the range of IADLs required for independence.

There are, however, several limitations to the design and interpretation of broad ability-level cognitive training described above [43]. First, over a century of research on skill acquisition has shown relatively narrow transfer and strong domain specificity for acquired skills [20]. In fact, sometimes a narrow training package may be more effective than training of general abilities, namely broad training, depending on the type of task and target outcome [33]. Given the range of interventions that have shown some efficacy, application of this knowledge to deploying cost-effective population-level interventions requires assessing their *comparative effectiveness*.

Second, relatively few intervention studies have assessed independence using metrics other than cognitive ability measure proxies. For example, many studies have used laboratory task outcomes such as the Useful Field of View (UFOV) test - as a predictor of driving crashes [22] - rather than using performance data from real or simulated driving. Third, practice effects on cognitive measures that are repeated from baseline to post-training test can make it difficult to estimate true change, although increased participant age tends to minimize practice effects and alternate form use can almost eliminate practice effects for some tests [11], though not for all tasks during relatively long periods of intervention [e.g., 37, 38, 39]. Finally, placebo effects, particularly expectation effects, are a serious threat to interpreting intervention studies [8].

[figure not shown]

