This randomized trial was designed to compare the effectiveness of broad and directed (narrow) technology-based training on basic perceptual and cognitive abilities in older adults and on the performance of simulated tasks of daily living. Participants were randomly assigned to four training conditions: (1) a brain game; (2) a video game; (3) IADL training for both fraud avoidance and driving; or (4) an active control condition, involving puzzle solving. This trial seeks to provide guidance not just about what works, but also what works best for a given investment (i.e., time, money) in older adults. The current trial was specifically designed to

address the several methodological limitations mentioned above, including: (1) the development of direct measures of IADL performance, targeting areas related to risks for catastrophic failure (e.g., crashes in driving, losing financial resources to fraud); (2) the use of alternate forms to provide more precise estimates of treatment effects (for both cognitive and IADL measures); (3) inclusion of an active control condition; and (4) measurement of expectation effects (as recommended in [43]). In this paper, we provide a primer to the design of this trial and describe the baseline characteristics of our sample.

Overall design

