This trial is registered on *ClinicalTrials.gov* (Identifier#: NCT03141281). The trial is a single-site randomized controlled trial (RCT), conducted at Florida State University (FSU; Tallahassee, FL), one of four funded sites of the National Institute of Aging Center for Research and Education on Aging and Technology Enhancement (CREATE). Following a telephone screening and baseline assessments, eligible participants were randomized into one of four conditions: (1) Posit Science's BrainHQ; (2) Rise of Nations, a PC-based video game; (3) Instrumental Activities of Daily Living (IADL) training, on both AARP's Driver Safety Course, and a Financial Fraud training course developed for this intervention; (4) active control group, playing a suite of three tasks (i.e., Sudoku, crossword puzzles, and word search). Once participants were assigned to a condition, they received a laptop with specialized software for their condition. Participants received in-lab training designed to encourage familiarity with how to operate a laptop, and the necessary components for their task. Participants were asked to train on their assigned condition for four weeks at home, and return for two scheduled days of post-training assessments, as well as a follow-up assessment at 12 months. The overall study design and contact schedule is summarized in Figure 1. The trial had highly standardized protocols for recruitment, screening, assessment, intervention administration (including manuals sent home with participants), and data transfer from intervention devices. The Institutional Review Board (IRB) at Florida State University, approved the protocol for this trial.

Timeline & Project Flowchart

CERTIFICATION OF ASSESSORS AND INTERVENTIONISTS

All assessors and interventionists who obtain informed consent and/or administer study protocols have already completed CITI training course. In addition, undergraduate and post-bachelor's research assistants have been taught proper procedures and will be directly supervised by the study PI's or someone listed as a co-investigator of research staff in FSU IRB.

SAMPLE RECRUITMENT & RETENTION

Inclusion & Exclusion Criteria

Inclusion

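### The per-hour comparison divides raw change by reported hours without removing change shared by all arms, so unequal hours can create a false per-hour difference

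*SAP*

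**What the plan says.** SAP, COMPARATIVE EFFECTIVENESS ANALYSES, item 1 defines the outcome for all primary and secondary variables as "Immediate gain scores (post-training - baseline)/hours of reported training" and compares it across arms. Item 2 uses "Long-term gain scores (1-year follow-up - baseline)/hours of reported training". Neither item names a test, and neither subtracts the control-arm change before dividing.

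The SAP's efficacy section separately plans four arms "x 2 times of measurement (baseline, post-training) ANOVAs (or ANCOVAs) for the following primary variables", with matching analyses for the secondary variables and for one year. These use undivided scores.

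The Protocol says the trial should show "what works best for a given investment (i.e., time, money) in older adults". Its opening background section warns that "practice effects on cognitive measures that are repeated from baseline to post-training test can make it difficult to estimate true change". The same sentence continues "although increased participant age tends to minimize practice effects and alternate form use can almost eliminate practice effects for some tests", but adds "though not for all tasks during relatively long periods of intervention". Alternate forms are listed as a design feature for both cognitive and IADL measures.

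**The concern.** The puzzle control exists so that change unrelated to training drops out when arms are compared. In items 1 and 2 each person's change is divided by that person's own hours before any comparison, so the shared part no longer drops out unless hours have the same distribution in every arm. An arm could then look more efficient only because its members reported fewer hours.

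Items 1 and 2 are the only SAP analyses that bring training time into the comparison, so they carry the Protocol's question about return on time invested. A wrong ranking there would go to the trial's central practical message.

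**Working it through.** The documents supplied give no sample size, alpha, effect size or expected hours by arm, so there is no planned figure to reproduce.

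**1. Algebra.** Let every person's change be c plus random error, with no training effect and error independent of hours h. The mean score in arm A is c × E_A[1/h]. The difference between arms A and B is c × (E_A[1/h] − E_B[1/h]), which is zero only if c = 0 or the two means of 1/h agree. For undivided change it is c − c = 0, so the arm-by-time ANOVAs are unaffected.

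**2. Hours in the Protocol.**
- Telephone script for recruitment: every recruit is told roughly 20 h.
- Brain HQ and Rise of Nations training protocols: 1 h × 5 days × 4 weeks = 20 h.
- IADL arm by stated pace (IADL1 Training Protocol): 0.5 × 4 × 4 = 8 h to 1 × 5 × 4 = 20 h. No total is given.
- IADL arm by course length (My Account Page; Finances & Fraud Education), each course taken twice: 2×6 + 2×5 = 22 h to 2×6 + 2×6 = 24 h.
- End of Lab Training Session says the last unit is not taken on the first pass. With 6 and 8 equal units assumed, the driving course is 6×5/6 + 6 = 11 h. The fraud course is 5×7/8 + 5 = 9.375 h to 6×7/8 + 6 = 11.25 h. The total is 20.4–22.25 h.
- AARP Unit 1 (1 h) is done in the lab, which leaves 19.4–21.25 h at home.
- Puzzle arm, and the IADL take-home schedule: not visible in the text supplied.

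Two arms are therefore set by time and one by content. Pace and course length agree only at the top of the pace range, and those passages need reconciling. The score uses reported hours, which may differ from any plan.

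**3. Simulation with no training effect.** Assumptions, none from the documents: 60 per arm; retest r = 0.7, so the SD of change is √(2(1−0.7)) = 0.77; hours SD 20% of the mean; the other three arms at 20 h; one-way F test on change/hours; 20,000 runs per cell. The mean score of a 20 h arm at c = 0.3 is 0.0157 SD/h.

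| IADL mean hours | IADL mean score, c = 0.3 (SD/h) | False positives, c = 0.3 | IADL ranked first of four: c = 0.3 / 0.1 / 0 |
|---|---|---|---|
| 13.5 | 0.0233 | 13.6% | 64% / 41% / 31% |
| 16 | 0.0196 | 7.6% | 47% / 34% / 28% |
| 19.4 | 0.0162 | 5.0–5.4% | 28% / 26% / 26% |
| 22.25 | 0.0141 (0.0157 × 20/22.25) | 5.0–5.4% | 16% / 21% / 24% |
| 24 | 0.0131 | 6.1% | 11.5% / 18% / 22% |

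The 5.0–5.4% is the range over 18–22.25 h. The 13.5 h row is the midpoint of the stated pace (0.75 × 4.5 × 4). Undivided change gives 4.7–5.4% false positives and about 25% ranked first throughout.

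**4. Sensitivity of the false-positive rate.**
- c = 0.1: 5–6% from 13.5 to 24 h.
- Shared decline of 0.3: 4.9–5.9% at 18–24 h, 7.4% at 16 h, 13.7% at 13.5 h.
- n from 50 to 80 and r from 0.5 to 0.8, at c = 0.3: 5.0–5.3% at 19.4 h, 6–9% at 16 h, 9–22% at 13.5 h, 6–7% at 24 h.
- 8 h at c = 0.3: 46%. This is an extreme; it needs both minimums of the stated pace and is hard to square with two passes through the courses.

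**The case against.** At the hours the documents plan, the test is almost unharmed: 5.0–5.4% at 18–22.25 h and 6.1% even at 24 h. A material false-positive rate needs both a sizeable shared change and an arm well short of 20 h. At c = 0.2, rates are only 6.0% at 16 h and 8.8% at 13.5 h. The Protocol itself expects age and alternate forms to shrink practice effects. The SAP says only that arms will be compared and plans no choice of a winner. Some of the ranking distortion is unequal variance: 31% at 13.5 h with c = 0. A spurious per-hour difference would also usually sit beside a null arm-by-time interaction.

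Most of this stands as a limit on size. It does not remove the defect. The documents give no value for c, alternate forms do not help every task by the Protocol's own account, and item 2 spans a year in which ageing may also act. Ranking is close to what the stated aim asks, and at c = 0.3 it moves to 16% at 22.25 h, within the range implied by course length. The SAP does not make the per-hour comparison conditional on the interaction. The hidden puzzle-arm hours and IADL schedule are no evidence of imbalance; they leave its likelihood unknown.

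**Conclusion.** The concern holds, in conditional form. If reported hours differ by arm and some change is shared by all arms, items 1 and 2 are biased; if either condition fails, they are not biased. With all arms at about 18–22 h a significance test barely moves. With one arm at 16 h (20% fewer) or 13.5 h (32.5% fewer) and c = 0.3 SD, false positives rise to 7.6% and 13.6%, and the chance that this arm ranks first rises from 25% to 47% and 64%. These sizes rest on the assumed c, sample size, retest correlation and spread of hours. The point should be fixed because the remedy needs no new data and does not depend on knowing c or the hours in advance. Confidence is medium, because neither quantity is in the documents.

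**What to change.** Keep the arm-by-time ANOVAs. In items 1 and 2, replace the person-level ratios as follows.

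- For each active arm, estimate the baseline-adjusted mean difference from the puzzle control and divide it by that arm's mean hours.
- Compare the three ratios pairwise, with intervals from one joint bootstrap that resamples all four arms. This carries the shared control and the uncertainty in hours.
- Include every randomised participant with an observed outcome. Those reporting zero hours have no defined score under the present formula. State how missing outcomes are handled.
- Report mean and SD of hours by arm, and whether they are reported or logged. The Protocol's Overall design mentions "data transfer from intervention devices", so logged hours may exist.

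**Check of the fix** (400 resamples, 2,000 trials per cell, IADL at 8–24 h). Single contrasts reject 4.4–7.4% and a joint max-t test 4.9–6.8% across a shared gain of 0.3, a shared decline of 0.3, and a shared gain with an equal true effect per hour in all active arms. That is slightly above 5% but does not depend on hours. At c = 0.3 the chance that IADL ranks first of the three active arms (33% expected), present score against fix, is 69% v 38% at 13.5 h, 55% v 36% at 16 h, 37% v 34% at 19.4 h and 18% v 32% at 24 h.

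**Cost.** SAP wording and a short bootstrap. Each ratio against control has a standard error about √2 = 1.41 times that of the arm's own raw ratio. The puzzle arm loses its own per-hour score, and the ratios then mean gain beyond puzzles, so any benefit of puzzles is subtracted too. Contrasts between active arms widen little, by √[(a² + b² + (a−b)²)/(a² + b²)] with a and b the reciprocals of the two arms' hours: 0% at equal hours, 1% at 16 or 24 against 20 h, and 4% at 13.5 against 20 h.
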